11.2. Trial Flow Chart

Evaluations	Screening Visit	MRI Visit	¹⁸ F-AV-1451 Imaging Visit	Follow-Up Phone Call
Updated Medical History	X		X	
Updated Concomitant Meds	X		X	
ECG	X			
Vital Signs			X	
Safety Labs ^a	X			
Urine Pregnancy Test			X	
MRI of the Brain		X		
PET Brain Scan			X	
Follow-up Phone Call				X
Evaluation by Physician/Designee	X		X	
Adverse Events	X	X	X	X
Serious Adverse Events	X	X	X	X

^aSafety labs to be collected any time between consent and ¹⁸F-AV-1451 Injection at Imaging Visit

INVESTIGATOR’S AGREEMENT TO PROTOCOL

Protocol: An open label, multicenter study evaluating the imaging characteristics of a follow up ¹⁸F-AV-1451 scan in subjects that participated in the confirmatory cohort of ¹⁸F-AV-1451-A05

Date and Version: 22 March 2016, Final

I agree to conduct the study according to this protocol and to comply with its obligations, subject to ethical and safety considerations and all applicable regulations (ICH, CFR).

I shall not disclose the confidential information contained in this protocol or any results obtained from the study, except for publication in accordance with Section 9 of this protocol, without written authorization from Avid.

Printed Name

Date

Signature

1. INTRODUCTION

Flortaucipir has been developed as a positron emitting radiopharmaceutical for in vivo imaging of tau protein aggregates (Xia et al., 2013). Autoradiography results using tissue sections from human brains showed a strong signal in the grey matter of cortical slices from tau positive brains but weak or no binding in tau negative, A β positive, or tau and A β negative tissue.

The overarching goal of this protocol is to further investigate the spectrum of PET imaging results with flortaucipir in patients with cognitive decline. To accomplish this goal, the protocol will investigate longitudinal flortaucipir results in patients with cognitive complaints ranging from mild cognitive impairment (MCI) to mild and moderate Alzheimer's disease (AD).

The purpose of this statistical analysis plan (SAP) is to describe the statistical analyses for the analyses of the protocol. The SAP should be read in conjunction with the protocol.

2. STUDY OBJECTIVES

2.1. Primary Objective

The primary objectives of this protocol is to assess longitudinal change of tau deposition as measured by flortaucipir over time.

3. STUDY DESIGN

3.1. Study Design

This is a phase 2 study, open label, multicenter study in subjects that participated in the confirmatory cohort of ¹⁸F-AV-1451-A05 evaluating longitudinal change of tau uptake as measured by flortaucipir Standard Uptake Value Ratio (SUVR). As subjects from the ¹⁸F-AV-1451-A05 confirmatory cohort complete the ¹⁸F-AV-1451-A05 study, they will be presented with the opportunity to participate in this longitudinal study.

All subjects will provide informed consent before starting any study procedures.

3.2. Study Treatments and Assessments

3.2.1. Trial Flow Chart

Evaluations	Screening Visit	MRI Visit	Flortaucipir Imaging Visit	Follow-Up Phone Call
Updated Medical History	X		X	
Updated Concomitant Meds	X		X	
ECG	X			
Vital Signs			X	
Safety Labs ^a	X			
Urine Pregnancy Test			X	
MRI of the Brain		X		
PET Brain Scan			X	
Follow-up Phone Call				X
Evaluation by Physician/Designee	X		X	
Adverse Events	X	X	X	X
Serious Adverse Events	X	X	X	X

^aSafety labs to be collected any time between consent and ¹⁸F-AV-1451 Injection at Imaging Visit

3.3. Randomization and Blinding

This is an open label, non-randomized study. All subjects who qualify for the study and sign informed consent will receive a single IV bolus of flortaucipir.

3.4. Sample Size Justification

This study is estimated to enroll about 100 subjects from A05 confirmatory arm. Current analyses with A05 exploratory arm data showed that for subjects met A05 confirmatory arm enrollment criteria (MCI or demented, Mini Mental State Exam (MMSE) between 20 and 27), flortaucipir SUVR on average changed 0.0527 (SD=0.0970) for amyloid positive subjects at 9 months follow up. Assume a similar amyloid positivity to A05 exploratory arm (~60%), and assume the change of flortaucipir SUVR is linear, this study is expected to have approximately 60 amyloid positive subjects and the mean change of flortaucipir SUVR is expected to be 0.105, with a 95% confidence interval (0.0635, 0.1473).

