
Statistical Methods:
 
Descriptive statistics will be used to summarize the change in AV-1451 from A05 baseline (Change From Baseline; CFB) for the AV-1451 SUVR from the combination region and individual sub-regions. Analysis of covariance (ANCOVA) adjusting for baseline AV-1451 SUVR level and age will be applied to compare the least square (LS) mean tau CFB by clinical diagnosis groups (MCI vs. AD), amyloid status (AB+ vs. AB-) and the interaction of these two factors. The relationship between AV-1451 SUVR CFB and cognitive function assessments CFB will also be explored using ANCOVA models.
		

TABLE OF CONTENTS

1.	INTRODUCTION	8
2.	TRIAL OBJECTIVES	11
3.	SPONSOR, INVESTIGATOR(S) AND OTHER PARTICIPANTS	11
4.	TEST DRUG AND CONTROL AGENTS	12
4.1.	Descriptive Name: ¹⁸ F AV-1451	12
4.2.	Radioactive Labeling	12
4.3.	Decay Characteristics	12
4.4.	Formulation and Dose ¹⁸ F-AV-1451 Injection	12
4.5.	Packaging ¹⁸ F-AV-1451 Injection	13
4.6.	Storage and Handling ¹⁸ F-AV-1451 Injection	13
5.	INVESTIGATIONAL PLAN	13
5.1.	Overall Design and Plan of Trial	13
5.2.	Planned Dosage and Duration of Treatment	14
5.2.1.	Dosage and Administration	14
5.2.2.	Rationale for Dosages	14
5.3.	Selection of Subjects	14
5.3.1.	Inclusion Criteria	14
5.3.2.	Exclusion Criteria	15
5.4.	Prior and Concomitant Therapy	15
5.5.	Removal of Subjects from Trial	15
5.6.	Premature Termination of Trial/Closure of Center	16
6.	WARNINGS/PRECAUTIONS	16
7.	PROCEDURES AND METHODS	16
7.1.	Assessment Periods	16
7.1.1.	Screening Visit:	17
7.1.2.	MRI Visit:	17
7.1.3.	PET Imaging Visit:	17
7.2.	Observations and Measurements	18
7.3.	Protocol for Image Collection	19
7.4.	Good Clinical Practice and Monitoring	19
7.5.	Informed Consent and Subject Information	19

7.6. Documentation..... 20

7.7. Adverse Events (AE) 20

7.7.1. Adverse Event Monitoring 21

7.7.2. Adverse Event Definitions..... 21

7.7.3. Adverse Event Documentation 23

7.7.4. Reporting of Serious Adverse Events..... 23

8. STATISTICAL ANALYSIS 23

8.1. General Statistical Considerations 23

8.1.1. Sample Size Estimation 24

8.2. Efficacy Analysis..... 24

8.3. Safety Analysis 24

8.4. ¹⁸F-AV-1451 Image Analysis 25

9. USE OF DATA AND PUBLICATION 25

10. INVESTIGATOR’S REGULATORY OBLIGATIONS 26

10.1. Institutional Review Board (IRB)..... 26

10.2. Informed Consent 26

10.3. Protocol Adherence 26

10.4. Documents Necessary for Initiation of the Trial 26

10.5. Investigational Product Control..... 27

10.6. Data Collection 27

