8.1.1. Sample Size Estimation

This study is estimated to enroll about 100 subjects from A05 confirmatory arm. Current analyses with A05 exploratory arm data showed that for subjects met A05 confirmatory arm enrollment criteria (MCI or demented, MMSE between 20 and 27), AV1451 SUVR on average changed 0.0527 (SD=0.0970) for amyloid positive subjects at 9 months follow up. Assume a similar amyloid positivity to A05 exploratory arm (~60%), and assume the change of AV1451 SUVR is linear, this study is expected to have approximately 60 amyloid positive subjects and the mean change of AV1451 SUVR is expected to be 0.105, with a 95% confidence interval (0.0635, 0.1473).

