5. CHANGES FROM PROTOCOL

The following changes from the protocol are reflected in this SAP.

- With continued development and accumulated knowledge, Multi-Block Barycentric Discriminant Analysis (MUBADA) SUVr instead of Combination ROI, will be used as the global measurement of tau deposition.

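### SAP 3.4 carries the protocol's change, SD and interval over unchanged after MUBADA SUVr replaced the Combination ROI, so the SAP's only precision statement is not shown to describe its primary endpoint

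*SAP*

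**What the plan says.** The Statistical Methods part of the protocol synopsis summarises change from A05 baseline "for the AV-1451 SUVR from the combination region and individual sub-regions". The protocol does not mention MUBADA.

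Protocol 8.1.1 bases the study size on A05 exploratory-arm data, in which "AV1451 SUVR on average changed 0.0527 (SD=0.0970) for amyloid positive subjects at 9 months follow up". It names no region.

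SAP 5 declares one change from the protocol: MUBADA "SUVr instead of Combination ROI, will be used as the global measurement of tau deposition". SAP 14.1 then makes MUBADA SUVr change from A05 baseline the primary variable, and 14.2.1 tests it between AD and MCI and between amyloid-positive and amyloid-negative subjects.

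SAP 3.4 restates the protocol paragraph: "flortaucipir SUVR on average changed 0.0527 (SD=0.0970) for amyloid positive subjects at 9 months follow up". Under the instruction to "assume the change of flortaucipir SUVR is linear", it gives an expected change of 0.105 with a 95% interval of 0.0635 to 0.1473, and says that "this study is expected to have approximately 60 amyloid positive subjects". The tracer name is updated and MMSE is spelled out. No region is named, and MUBADA is not mentioned. The SAP has no other power, precision or sample-size statement.

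**The concern.** A mean change and its SD belong to a particular region of interest. Someone who reads SAP 3.4 together with 14.1 will take 0.105 as the expected MUBADA change and the interval as the expected MUBADA precision. Nothing in the SAP supports that. The figures already stood in a protocol dated 22 March 2016, whose global measure was the combination region, and SAP 5 attributes the move to MUBADA to knowledge gained later. SAP 5 records the change of measure but does not say what it does to 3.4.

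What is at stake is limited. Section 3.4 is the plan's only numerical expectation for its primary objective. If a report set the observed MUBADA change beside 0.105, it might be comparing two different measures without saying so.

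**Working it through.** **Inputs.** Mean 9-month change 0.0527, SD 0.0970, about 60 amyloid-positive subjects, linear change, stated result 0.105 (0.0635, 0.1473). All are in SAP 3.4 and, with the same digits, in Protocol 8.1.1. The 18-month horizon is implied: 0.105 is twice the 9-month change, and SAP 6.2 uses 18-month A05 data.

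**Step 1: compare the two sections.**

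| Item | Protocol 8.1.1 | SAP 3.4 |
|---|---|---|
| 9-month mean change | 0.0527 | 0.0527 |
| 9-month SD | 0.0970 | 0.0970 |
| Amyloid-positive subjects | about 60 | about 60 |
| Expected change | 0.105 | 0.105 |
| Stated 95% interval | 0.0635 to 0.1473 | 0.0635 to 0.1473 |
| Region named | no | no |
| Global measure in that document | combination region | MUBADA |

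**Step 2: reproduce the printed figures.**

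- Mean: 2 × 0.0527 = 0.1054, which is also the midpoint of the printed interval.
- Printed half-width: (0.1473 − 0.0635)/2 = 0.0419.
- SD on the doubled scale: 2 × 0.0970 = 0.1940. Standard error: 0.1940/√60 = 0.02505.
- With t(0.95, 59) = 1.671: half-width 0.0419, limits 0.0635 and 0.1473. Both match to four decimals. This is a two-sided 90% interval.
- With t(0.975, 59) = 2.001, the two-sided 95% quantile: half-width 0.0501, limits 0.0553 and 0.1555. With z = 1.960: 0.0563 and 0.1545. Neither matches.
- Other SD scalings at n = 60 and two-sided 95% (z) also fail: SD 0.0970 gives 0.0809 to 0.1299, SD × √2 gives 0.0707 to 0.1401, and SD × √3 gives 0.0629 to 0.1479.

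If n is not held at 60, an undoubled SD of 0.0970 with n = 23 and t(0.975, 22) has half-width 0.0419 and also rounds to the printed limits. The documents mention no sample of 23, and that calculation would double the mean without doubling the SD. The 90% reading is the one that uses only the section's own inputs.

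**Step 3: what MUBADA precision could be.** Neither document gives a MUBADA mean or SD, so no single figure can be computed. Half-width = 2.001 × SD/√60, with the 18-month MUBADA SD assumed as a multiple of 0.194:

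| Assumed multiple | SD | 95% half-width |
|---|---|---|
| 0.75 | 0.1455 | 0.038 |
| 1 | 0.194 | 0.050 |
| 1.5 | 0.291 | 0.075 |

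The printed half-width is 0.042. The multiples show how precision scales with the SD and are not estimates for MUBADA. The centre of the interval is unknown as well.

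**Step 4: what the interval is about.** Section 3.4 describes the mean change in one group, the amyloid-positive subjects. The hypotheses in 14.2.1 are differences in LS means between groups, from an ANCOVA adjusted for baseline SUVr and age. Even with MUBADA inputs, 3.4 would not give the precision of those contrasts.

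**The case against.** The strongest reply has three parts.

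First, no region is attached to 0.0527 (SD 0.0970) in either document. A reader might infer that the figures are documented combination-region values and therefore wrong for MUBADA. The documents do not go that far. Protocol 8.1.1 and 8.2 say only SUVR, and 8.4 speaks generally of tau-rich regions. That the figures are not MUBADA values is a strong inference from their date and from the declared switch. This part stands and sets the wording: not shown to describe the endpoint. The gap remains on either reading, because if the figures are MUBADA values, the SAP should say so.

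Second, the two regions might behave alike. That also stands: the size and direction of any difference are unknown.

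Third, nothing depends on 3.4. Recruitment is limited to A05 confirmatory completers, SAP 16 plans no interim analysis, 14.2 sets no success threshold, and no passage judges the observed change against 0.105. A reader might infer that the study's result could not be interpreted. The documents do not support that, because the estimates, contrasts and confidence intervals in 14.2.1 are unaffected.

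The reply does not remove the need for a correction. SAP 5 discloses the change of measure but leaves 3.4 looking current, and the interval's label does not agree with its own inputs.

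**Conclusion.** The point holds as a gap in a stated design figure. SAP 3.4 repeats figures that predate the move to MUBADA, does not say which region they describe, and is the only precision statement in the SAP. Its interval, taken with the section's own mean, SD and n = 60, is a two-sided 90% interval labelled 95%. The 95% half-width is 0.050 instead of 0.042.

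This rests on two inferences: that the figures were not computed on MUBADA, and that the interval used the doubled SD with n = 60. The range of 0.038 to 0.075 for MUBADA is purely by assumption. No test, estimate or decision rule changes, so the correction is desirable, not essential.

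**What to change.** Restate SAP 3.4 with the 9-month mean, SD and number of subjects for MUBADA SUVr, from A05 exploratory amyloid-positive subjects who meet the confirmatory criteria. Add the implied 18-month mean and a correctly computed 95% interval.

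If those scans cannot be requantified, keep the figures but:

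- state that they predate the switch to MUBADA, and name the region they describe;
- either change the limits to 0.0553 and 0.1555 or change the label to 90%;
- say that precision is not established for MUBADA or for the between-group contrasts in 14.2.

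The first option costs one summary of A05 exploratory scans plus SAP wording. The second costs a few sentences. The stated precision may become less favourable: correcting the interval alone widens the half-width from 0.042 to 0.050.

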3.5. Subject Selection Criteria

Refer to Protocol Section 5.3, Selection of Subjects, for the detail of inclusion/exclusion details.

4. CLINICAL AND IMAGING ASSESSMENTS

4.1. Screening and Baseline Clinical Assessments

Screening assessments should take place at the time of the subject's final ¹⁸F-AV-1451-A05 study visit. All screening assessments should be performed within 30 days of the initial flortaucipir PET imaging session.

Screening assessments will include:

- Informed consent;
- Blood and urine samples will be collected for safety labs (may be collected any time prior to flortaucipir injection)
- Electrocardiogram (ECG);
- Updated medical history and concomitant medications.

4.2. MRI Visit

MRI should be acquired after subject consent is obtained, prior to the time of Flortaucipir Imaging Visit.

- MRI imaging including standard clinical sequences and volumetric MRI.

4.3. Flortaucipir PET Imaging Visit

It is preferable that the Flortaucipir PET imaging visit is performed within 30 days of the subject's final ¹⁸F-AV-1451-A05 study visit, but no later than 3 months from the final ¹⁸F-AV-1451-A05 study visit.

Flortaucipir PET Imaging Session:

- A physician or a licensed/credentialed medical professional (i.e., a PET technologist, imaging center nurse or a regional equivalent) designated by the site principal investigator must assess or evaluate the subject prior to administration of flortaucipir injection to determine if they are still suitable to undergo the scan. If a designee performs this activity, a physician must be available to provide medical consultation;
- For women of childbearing potential, a negative urine pregnancy test must be obtained;
- Vital signs will be taken at the following time points:
 - immediately prior to administration of flortaucipir injection
 - after completion of the PET scan, prior to discharge;
- Subjects will receive a single IV bolus injection of approximately 370 MBq (10 mCi) +10% of flortaucipir injection followed by a saline flush. At approximately 80 minutes post dose, a continuous 20-minute brain scan (4 acquisitions of 5 minute duration) will be obtained.;
- The injection site will be observed for excessive inflammation or damage to the surrounding tissue where the dose was injected;

- The subject will be requested to void after completion of the PET scan;
- Adverse events will be continuously monitored during the Flortaucipir Imaging Visit; Subjects who experience an adverse event will not be discharged from the imaging center until the event has resolved or stabilized;
- A physician or a licensed/credentialed medical professional (i.e., a PET technologist, imaging center nurse or a regional equivalent) designated by the site principal investigator must assess or evaluate the subject prior to discharge from the imaging center to evaluate the subject's readiness for discharge. If a designee performs this activity, a physician must be available to provide medical consultation.

4.3.1. Safety Follow-up/Phone Call

Each study subject (or caregiver/informant if applicable) will be contacted 2 or 3 business days after flortaucipir administration, but not prior to 48 hours post-injection, to collect any new adverse events. End of study for the purpose of adverse event reporting and study participation is defined as 48 hours after flortaucipir administration.

5. CHANGES FROM PROTOCOL

The following changes from the protocol are reflected in this SAP.

- With continued development and accumulated knowledge, Multi-Block Barycentric Discriminant Analysis (MUBADA) SUVr instead of Combination ROI, will be used as the global measurement of tau deposition.

6. DEFINITIONS AND CONVENTIONS

6.1. Data Conventions

All analysis will be performed using SAS version 9.2 or higher.

Data will be summarized using descriptive statistics (number of subjects [n], mean, standard deviation [SD], median, minimum (min), and maximum (max)) for continuous variables and using frequency count and percentage for discrete variables. Percentages will be rounded to one decimal place, except 100% will be displayed without any decimal places and percentages will not be displayed for zero counts.

The tables and listings will be numbered using a decimal system to reflect main levels of unique tables and listings and sub-levels of replicate tables and the listings with maximum two digits per level (e.g., Table XX.YY.ZZ...). Tables will be presented in CSR section 14, and thus will be numbered as 14.YY.ZZ. Baseline analysis will be reported in table series 14.1, efficacy analysis in series 14.2, and safety analysis in series 14.3. Listings will be presented in in CSR section 16, and thus will be numbered as 16.YY.ZZ. .

6.2. Definitions of Baseline and Follow-up

Baseline characteristics and demographics will be gathered from the AV-1451-A05 datasets for confirmatory cohort subjects who participated in AV-1451-A18. All other baseline data (i.e. electrocardiogram, and safety labs) will be reported from data collected from the AV-1451-A18 CRFs.

Efficacy analysis evaluating longitudinal change will require the use of the Baseline flortaucipir SUVr quantitation, and Baseline and 18 Month MMSE from the AV-1451-A05 datasets to calculate change.

Safety analysis involving change from baseline (CFB) calculations for vital signs will consider AV-45-A18 *Prior to Injection* values as baseline and *Prior to Discharge* as follow-up.

7. ANALYSIS POPULATIONS

7.1.1. Enrolled Population

Subjects who participated in the 18F-AV-1451-A05 confirmatory cohort, meet the inclusion/exclusion criteria of 18F-AV-1451-A18, have consented to be enrolled in this study, and have baseline data captured in the AV-1451-A05 eCRF database will consist of the enrolled population.

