8. STATISTICAL ANALYSIS

8.1. General Statistical Considerations

All statistical analyses will be performed using SAS® version 8.2 or higher.

Data will be summarized using descriptive statistics (number of subjects [N], mean, standard deviation [SD], median, quartiles, minimum, and maximum) for continuous variables and using frequency count and percentage for discrete variables. The demographic and baseline characteristics data will be summarized according to clinical group (healthy volunteers and subjects with cognitive impairment) at recruitment for all subjects in the safety population. Safety data will be summarized for all patients.

Subject listings of all data from the electronic case report forms (eCRFs) as well as any derived variables will be presented.

Additional details concerning statistical analyses will be included in the Statistical Analysis Plan (SAP).

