10.3. Protocol Adherence

The protocol must be read thoroughly and the instructions must be followed exactly. Where a deviation occurs, it must be documented, the sponsor/monitor informed, and a course of action agreed upon.

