7.1.2. Safety Analysis Population

The safety analysis population will consist of all enrolled subjects who received at least one injection of flortaucipir under the AV-1451-A18 protocol.

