7.1.3. Efficacy Analysis Population

This population includes all subjects in safety population for whom valid image data are available for the AV-45-A18 flortaucipir scan. All primary analyses will be based on this population.

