15. SAFETY AND TOLERABILITY ANALYSIS

The safety analysis population will be used for all safety outcomes. There will be no statistical comparisons between diagnosis or amyloid groups performed among the safety data.

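### The SAP ties the safety population to eligibility and A05 baseline data, so a dosed subject who fails either condition is left out of the safety tables, although Protocol 8.1 covers all patients

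*SAP*

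**What the plan says.** Three SAP definitions are chained.

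- **SAP 7.1.1** describes the enrolled population as A05 confirmatory-cohort subjects who "meet the inclusion/exclusion criteria of 18F-AV-1451-A18, have consented to be enrolled in this study, and have baseline data captured in the AV-1451-A05 eCRF database".
- **SAP 7.1.2** builds on it: "The safety analysis population will consist of all enrolled subjects who received at least one injection of flortaucipir under the AV-1451-A18 protocol".
- **SAP 15** then applies the result without exception: "The safety analysis population will be used for all safety outcomes".

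SAP 7.1.3 nests the efficacy population in the same set: "This population includes all subjects in safety population for whom valid image data are available" for the A18 scan.

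Protocol 8.1 states the scope of the safety summaries with no eligibility condition: "Safety data will be summarized for all patients". It also says: "Subject listings of all data from the electronic case report forms (eCRFs) as well as any derived variables will be presented". Protocol 8.3 adds that every subject with an SAE, or who discontinues because of an AE, is to be summarized.

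SAP 5 opens with "The following changes from the protocol are reflected in this SAP" and lists one item, the replacement of the combination region by MUBADA. It does not mention the safety population.

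**The concern.** A safety population normally consists of everyone exposed, because a subject's experience after dosing counts whether or not that subject should have been dosed. Here exposure is only the last of several conditions. Someone injected in breach of a criterion, for example a subject later found to have been taking a prohibited QT-prolonging drug (exclusion 2) or a recent investigational drug (exclusion 6), does not satisfy the SAP's definition of enrolled and so cannot enter the safety population.

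Such breaches are plausible.

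- The protocol foresees deviations in general (10.3): "Where a deviation occurs, it must be documented, the sponsor/monitor informed, and a course of action agreed upon". SAP 8 has a protocol-violation category among its discontinuation reasons. Neither removes a dosed subject from the safety data.
- Exclusion 2 names hypokalemia as a risk factor, yet safety labs may be drawn at any time up to the injection. The documents give no turnaround time for results.
- Protocol 5.4 lets medications begun before screening continue, while exclusions 2 and 6 bar subjects on certain drugs. Those passages need to be reconciled.

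At stake is whether the exposure and adverse-event tables describe everyone who received the tracer.

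**Working it through.** **Step 1: the sets.** The plan gives no figure to reproduce, so the check is on the definitions. For A05 confirmatory-cohort subjects:

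- Enrolled = meets A18 criteria AND consented AND has A05 eCRF baseline data (SAP 7.1.1)
- Safety = Enrolled AND injected under A18 (SAP 7.1.2)
- Hence Safety = meets criteria AND consented AND A05 data AND injected
- Efficacy = Safety AND valid A18 image data (SAP 7.1.3)

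A subject who was injected but fails the first or third condition is outside Safety, and therefore outside Efficacy.

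**Step 2: is such a subject restored elsewhere?** No SAP passage does so. SAP 8 puts the whole screened population in the disposition table, but that is not a safety table, and its completed/discontinued percentages use the safety population. SAP 5 declares no change. Protocol 10.3 deals only with documenting deviations.

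**Step 3: outputs affected.** Exposure (SAP 15.1), TEAEs with severity and relationship (15.2.2 to 15.2.5), SAEs (15.2.6), deaths (15.2.7) and vital signs (15.3), in both counts and denominators.

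**Step 4: comparison with the protocol.** Protocol 8.1 assigns demographic and baseline data to the safety population. In the next sentence it uses the wider term, all patients, for safety data. The set derived in step 1 is narrower than that wider term.

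**Step 5: illustration of size.** The documents give no breach rate p, so p is an assumption. N takes the two enrolment figures in the protocol: about 100 (8.1.1) and about 160 (synopsis). Expected number dropped = N × p. Chance of at least one = 1 − (1 − p)^N.

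| N | assumed p | expected dropped | chance of at least one |
|---|---|---|---|
| 100 | 1% | 1 | 1 − 0.99^100 = 63% |
| 100 | 5% | 5 | 1 − 0.95^100 = 99% |
| 160 | 1% | 1.6 | 1 − 0.99^160 = 80% |
| 160 | 5% | 8 | 1 − 0.95^160 = over 99% |

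**Step 6: effect on a rate (hypothetical inputs).** Suppose 3 of 100 injected subjects have a TEAE (3.0%) and 5 of the 100 are dropped.

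- If one of the 3 is among the 5, the table shows 2/95 = 2.1%.
- If none is, it shows 3/95 = 3.2%.
- If breaches are unrelated to AEs, the chance that at least one of the 3 is dropped is 1 − C(95,3)/C(100,3) = 1 − 138,415/161,700 = 14%.

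The reported rate can therefore move either way.

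**The case against.** **Enrolled may mean accepted at entry.** Protocol 5.3 frames the criteria as conditions for enrolling, SAP 3.3 has qualifying, consented subjects receive the injection, and suitability is reassessed before dosing. If enrolled means judged eligible at entry, a breach found later removes nobody. This is a reasonable reading and perhaps the intended one, but the SAP does not state it. The text requires that the criteria be met.

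**The conflict with Protocol 8.1 may be softer than it looks.** The sentence before the all-patients statement speaks of summaries by clinical group, so all patients could mean pooled over groups. The protocol also uses the term safety population without defining it and leaves detail to the SAP. This weakens the inference that a change went undeclared. Even so, nothing in the protocol conditions the safety summaries on eligibility.

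**The data do not disappear.** Listings of all eCRF data are still required, deviations are documented, and SAEs go to the safety recipient within 24 hours whatever the analysis set (Protocol 7.7.4, 10.7). This stands, and it confines the loss to the summary tables.

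**The A05-data condition will rarely matter.** Inclusion requires participation in and completion of A05. This also stands.

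**Stronger readings that a reader might infer.**

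- *AE incidence is biased downward.* That requires ineligible subjects to have more AEs than others, which no passage shows.
- *A QT signal would be hidden.* Protocol section 1 links the QT exclusions to the positive hERG assay and to limited human data, but it also reports no QT prolongation in dogs up to 50 times the maximum human dose. The only scheduled ECG is at screening, and SAP 9.2 plans only a listing of it. No post-injection QTc is scheduled that a table could omit. A clinical AE in such a subject remains possible.

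**Conclusion.** The point holds as an inconsistency in the definitions. Followed as written, SAP 7.1.1, 7.1.2 and 15 leave some exposed subjects out of the safety tables, contrary to the natural reading of Protocol 8.1 and without an entry in SAP 5.

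Its size cannot be stated from the documents. The counts in the table rest on an assumed breach rate of 1% to 5%, and the rate example rests on hypothetical AE counts. The direction of any effect on AE rates is unknown.

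It should be fixed, but it is not critical. The sole objective is longitudinal change in tau, the safety analysis makes no comparisons between diagnosis or amyloid groups, and each subject receives one tracer injection. A reader might also conclude that the efficacy population is wrong because it inherits the exclusion. The documents do not support that: leaving ineligible subjects out of an efficacy analysis can be a legitimate choice. What is missing is a statement that this was chosen for its own sake and is not a by-product of the nesting.

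**What to change.** - **SAP 7.1.2:** define the safety population as all subjects who received any flortaucipir injection under A18, regardless of eligibility deviations or availability of A05 baseline data.
- **Listings:** add a listing of eligibility deviations, so that the subjects concerned can be identified beside the tables.
- **SAP 7.1.3:** state separately whether ineligible subjects with valid scans stay in the efficacy population. This is a design choice for the sponsor, and it should be made before the analysis is run.
- **If enrolled was meant as accepted at entry:** say so in SAP 7.1.1. The redefinition in 7.1.2 removes the problem under either meaning.

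The cost is a few sentences in the SAP's population definitions, one listing and a SAP revision. It needs no new data. Because the change brings the SAP into line with Protocol 8.1, it needs no protocol amendment.
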